## 5.6.2 Overall Response Rate (ORR) and Clinical Benefit Rate (CBR)

Overall response rate (ORR) using irRC will be defined as the number and percent of patients with best overall response of irCR or irPR. ORR with two-sided 95% Clopper-Pearson exact CI will be provided. Both unconfirmed and confirmed response using irRC criteria will be reported. The overall response using irRC is derived from time-point response assessments as follows:

- Immune-related complete response (irCR), complete disappearance of all lesions (whether measurable or not, and no new lesions), confirmed by a repeat, consecutive assessment no less than 4 weeks from first documentation
- Immune-related partial response (irPR), decrease in tumor burden  $\geq 50\%$  relative to baseline, confirmed by a consecutive assessment at least 4 weeks from first documentation
- Immune-related stable disease (irSD), not meeting criteria for irCR or irPR, in absence of irPD
- Immune-related progressive disease (irPD), increase in tumor burden  $\geq 25\%$  relative to nadir, confirmed by a repeat, consecutive assessment no less than 4 weeks from first documentation

In confirmed ORR summary, patients with best response of unconfirmed irPR will be summarized as irSD.

Overall response rate (ORR) using IWG will be defined as the number and percent of patients with best overall response of CR or PR.

Clinical benefit rate (CBR) will be defined as the number and percent of patients with best overall response of complete response, partial response or stable disease. CBR using both irRC and IWG will be reported.

In addition, abscopal tumor reduction will be summarized.

Lesion assessment (lesion type, organ site, evaluation method, diameter, and lesion status), as well as patient overall response based on both irRC and IWG criteria for lymphomas at each visit and the best overall response, will be presented in a data listing.

Overall tumor response using irRC criteria for all tumor lesions, irradiated sites, non-irradiated sites and abscopal sites, and overall tumor response using IWG criteria for all tumor lesions will be summarized. Overall tumor response for the following subgroups will also be provided:

- Relapsed/Refractory Patients
- Treatment Native Patients
- Patients with MR (minor response)
- Patients with MR (minor response) and Decrease in Abscopal Lesions
- Patients with PD at Study Entry
- Patients with Guided Injection of G100
- Patients with Not Guided Injection of G100

MR (minor response) is defined as more than 25% decrease in tumor burden but less than the 50% that would make it a PR.

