### **4.3 Efficacy Evaluable Population**

The Efficacy Evaluable population includes all enrolled patients without major protocol deviations, who have received at least one injection of G100, and have had baseline and at least one post-baseline disease assessment.

The Efficacy Evaluable population will be used for the tumor response analysis based on irRC, including overall tumor response and time to disease progression (TTP).

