### 5.6.3 Duration of Response (DOR) and Duration of Clinical Benefit

Duration of response (DOR) is defined as the time interval between the date of the earliest qualifying confirmed/unconfirmed response using irRC and the date of disease progression (PD) or death for any cause, whichever occurs first. DOR in months is calculated as: (date of PD or death – date of first confirmed/unconfirmed irCR/CR or irPR/PR + 1)/30.4375. DOR analysis will include only patients with confirmed/unconfirmed response of irCR/irPR using irRC.

For patients who are alive without documentation of disease progression following the qualifying response, duration of response will be censored following the same rule defined for PFS.

Duration of clinical benefit is defined as the time interval between the date of the earliest qualifying confirmed/unconfirmed best response using irRC and the date of progression disease (PD) or death for any cause, whichever occurs first. Duration of clinical benefit in months is calculated as: (date of PD or death – date of first confirmed/unconfirmed irCR/irPR or irSD + 1)/30.4375. Duration of clinical benefit will include only patients with confirmed/unconfirmed response of irCR/irPR or irSD using irRC.

For patients who are alive without documentation of disease progression following the qualifying response, duration of clinical benefit will be censored following the same rule defined for PFS.

Median DOR and duration of clinical benefit with the corresponding two-sided 95% CI will be estimated using the Kaplan-Meier method in each treatment group. The Kaplan-Meier curves will be presented.

DOR and duration of clinical benefit data will be presented in listing.

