### 5.6.4 Progression-free Survival (PFS)

PFS is defined as time from date of first study treatment to date of first disease progression by irRC criteria, symptomatic deterioration, or death due to any cause, whichever occurs first. Progression-free survival (PFS) in months is calculated as: (date of first progression, symptomatic deterioration, or death (any reason) – date of first dose +1)/30.4375. The irRC modification requires a PD confirmation no less than 4 weeks from first documentation of progressive Disease (PD); once confirmed, the date of progression is defined as date of the first PD. In case of unconfirmed PD followed by symptomatic deterioration, the date of unconfirmed PD will be the date of progression. Patients without progression, symptomatic deterioration, or death are censored at the date of the last tumor assessment. If a patient begins a new anti-cancer therapy or has radiotherapy or surgery at a lesion site prior to confirmed progression (or death), the patient will be censored at the last assessment where the patient is documented as progression free prior to the intervention. Patients with two or more missing response assessments prior to a visit with progression (or death) will be censored at the last visit where the patient is documented to be progression free. Patients without disease assessment post-baseline will be censored at the first dose date. Table 7 below provides further details on how date of PFS event and date of PFS censoring are assigned.

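### SAP 5.6.2 has no rule for unconfirmed irPD, so read literally a patient whose only scan shows 25% or more growth is stable disease and counts as clinical benefit

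*SAP*

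**What the plan says.** SAP 5.6.2 derives overall response by irRC from time-point assessments. irPD is a 25% or greater increase over nadir, "confirmed by a repeat, consecutive assessment no less than 4 weeks from first documentation". irSD is whatever remains: "Immune-related stable disease (irSD), not meeting criteria for irCR or irPR, in absence of irPD". It carries no growth ceiling and no minimum duration. CBR counts "patients with best overall response of complete response, partial response or stable disease".

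For findings that lack confirmation, the section gives one explicit rule, for the confirmed ORR summary: "patients with best response of unconfirmed irPR will be summarized as irSD". It also promises that "Both unconfirmed and confirmed response using irRC criteria will be reported", without saying how an unconfirmed irPD appears in either version.

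One scan is enough to be analyzed. Under SAP 4.3, patients in the Efficacy Evaluable population must "have had baseline and at least one post-baseline disease assessment".

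Duration of clinical benefit (SAP 5.6.3) starts at the "date of first confirmed/unconfirmed irCR/irPR or irSD" and includes irSD patients. For PFS, SAP 5.6.4 does provide for the missing confirmation: "In case of unconfirmed PD followed by symptomatic deterioration, the date of unconfirmed PD will be the date of progression".

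Protocol Appendix B is not uniform:
- In its comparison table, the irRC row for SD is ruled out by a 25% increase over nadir.
- Its overall-response list repeats the residual wording used in the SAP.
- Its closing text asks for the second scan only when the patient is not deteriorating rapidly, and says irSD itself needs no confirmation.

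**The concern.** A patient can show clear growth at the first restaging and have no further assessment. The definitions leave that patient with no irCR, no irPR and no confirmed irPD, and so in the residual class. A scan that on its face shows growth is then tabulated as stable disease and as clinical benefit.

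The error runs in one direction, because it can only raise CBR. It also affects duration of clinical benefit and the irPR+MR+SD endpoint in the biomarker models of SAP 5.6.8. It may affect the IWG-based CBR as well, because protocol 5.5 uses irRC to determine PD there. For one subset of these patients, the PFS and CBR tables would describe the same scan in opposite ways.

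**Working it through.** **Plan's own figure.** The plan states no target or expected CBR, so there is none to reproduce. Its response-rate figures do reproduce by exact binomial:
- Part 2: P(0 of 12 | 0.20) = 0.8^12 = 6.9%.
- Part 4: P(≤5 of 22 | 0.40) = 7.2%, and P(≤5 of 22 | 0.20) = 73.3%.
- Part 5: P(≥5 of 20 | 0.32) = 81.7% (stated as 82%), and P(≤4 of 20 | 0.40) = 5.1%.

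All of these count objective or complete responses only. Moving a patient between irSD and irPD changes none of them.

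**Step 1: apply the definitions to example histories.** Changes are in tumor burden against baseline, with scans at least 4 weeks apart. Baseline is the nadir in each case.

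| Post-baseline scans | SAP 5.6.2, literal | In CBR? | Appendix B table |
|---|---|---|---|
| +10% only | irSD | yes | SD |
| +30% only | irSD | yes | neither SD nor PD |
| +80% only | irSD | yes | neither SD nor PD |
| +30%, then +40% | irPD | no | PD |
| +30%, then +10% | irSD | yes | SD |

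The second and third rows are the problem. The last row is irRC working as intended: early growth that is not borne out later.

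**Step 2: follow the +30%-only patient into PFS** (SAP 5.6.4 and its Table 7).

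| What follows the scan | PFS | CBR |
|---|---|---|
| Symptomatic deterioration | event, dated to that scan | benefit |
| Death before the next assessment | event, dated to death | benefit |
| New anti-cancer therapy before confirmation | censored at the last progression-free assessment | benefit |
| None of these, and no later scan | censored at the last assessment | benefit |

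Only the first row dates a PFS event to the very scan that CBR counts as benefit.

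**Step 3: duration of clinical benefit.** SAP 5.6.3 computes (PD or death date − date of first irCR, irPR or irSD + 1)/30.4375. If the PFS dating of unconfirmed PD were carried over, the two dates would coincide and the result would be 1 day, or 1/30.4375 = 0.03 months. However, 5.6.3 imports only the PFS censoring rule, so this value is an inference.

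**Step 4: size.** Each such patient shifts CBR by 100 × 1/N percentage points, using planned sizes.
- Part 2 arm: 1/12 = 8.3.
- Part 5 expansion: 1/20 = 5.0.
- Part 4: 1/22 = 4.5.
- Part 3: 1/25 = 4.0.

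The number of such patients is not given. Assuming 1 to 3 of 22, the shift is 4.5 to 13.6 points. As an illustration at 3 patients, 17/22 = 77.3% becomes 14/22 = 63.6%.

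**The case against.** The strongest reply is that irPD is also a time-point label. Appendix B assigns time-point response after irPD has been excluded, and speaks of a patient classed as irPD at an assessment before confirmation. Since SAP 5.6.2 builds overall response from time-point assessments, the absence of irPD could be read to exclude any scan over the threshold. A sensible programmer might do exactly that. This reading is available, but the irPD entry in SAP 5.6.2 includes the confirmation, and nothing there requires the other reading. The conflict within Appendix B is a reason to settle the point in the SAP.

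Second, such patients may be few. The schedules of events require progression to be confirmed by CT or MRI, eligibility requires ECOG 0 or 1 and a life expectancy of at least 6 months, and patients with PD not needing immediate therapy may be retreated on study and so can be rescanned. This stands. A reader might infer that the fastest progressors rarely get a confirming scan and that CBR is inflated in every part. The documents give no such frequency, and CBR rises only in groups where such a patient occurs.

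Third, CBR drives no stated decision, and the spider and waterfall plots and visit-level listings would show the growth. This also stands and limits the consequence. In addition, SAP Section 9 reports that the sponsor terminated the study, so the planned sizes may not have been reached.

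Finally, a reader might infer that every such patient has a PFS event on the scan date together with one day of benefit. SAP 5.6.4 supports the PFS event on the scan date for symptomatic deterioration only, and the one-day duration is not stated anywhere.

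**Conclusion.** The point holds as a definitional fault in SAP 5.6.2. Taken as written, it places a patient whose only post-baseline assessment(s) meet the 25% increase, with no later assessment, in irSD and therefore in CBR, duration of clinical benefit and the irPR+MR+SD endpoint. That contradicts the irSD row of the Appendix B table. It also drops the appendix's exception for rapid deterioration.

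The effect per patient is fixed by arithmetic, at 4.0 to 8.3 points over the planned group sizes. The total effect depends on a count that the documents do not supply. The conclusion rests on the literal reading of 5.6.2. If the analysis were programmed on the time-point reading, the misclassification would not occur, but the SAP would still not say so. The direct contradiction with PFS is confined to unconfirmed PD followed by symptomatic deterioration. The point does not extend to ORR or to any stated futility or signal rule.

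**What to change.** Amend SAP 5.6.2 as follows, and reconcile the Appendix B table and list with it.

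1. Require for irSD at least one post-baseline assessment that does not itself meet the 25% increase over nadir, in line with the Appendix B table.
2. Put patients whose only assessment(s) meet the increase, with no later assessment, in a separate class labeled unconfirmed irPD / not evaluable. Keep them in the denominator, and leave them out of the CBR numerator, duration of clinical benefit and the irPR+MR+SD endpoint.
3. Within that group, count patients with symptomatic deterioration as irPD. This agrees with the Appendix B exception and with SAP 5.6.4.
4. State that a later scan not showing the increase still makes the patient irSD, so that the protection against inflammatory growth is kept.

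Labeling every single-scan patient irPD would go too far, because it would also capture simple loss to follow-up and would set aside the reason irRC was chosen.

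The cost is a few sentences, one extra table row and the reconciliation with Appendix B. CBR becomes slightly less favorable if such patients exist. SAP Section 1 already allows justified, documented departures from the plan.

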### **5.6.8 Immune Response and Biomarker Analyses**

All patients who have received at least one injection of G100 and have available immunohistochemistry (IHC), nanostring, or T cell receptor (TCR) data will be included in the biomarker analysis.

Anti-tumor cellular immunity (CD4, CD8 T cell, CD20, CD68, NKp46, FoxP3, CD8/CD4 ratio, CD8/FoxP3 ratio) by immunohistochemistry (IHC) will be explored. Post/pre treatment ratio will be summarized by treatment, and by subgroups of interest (irPR vs non-responder, pre-TLR4 $\geq$ 50% vs <50%, treatment naïve, relapsed/refractory patients, prior line of therapy 0-2 vs  $\geq$ 3). Post and pre treatment values will be compared using signed-rank test to identify significant changes post treatment. Association between clinical endpoints (irPR, irPR+MR, irPR+MR+SD, abscopal best % change better than -25%) and cellular immunity by immunohistochemistry will be explored using a logistic regression model for all dosed patients, and by treatment. Association between response (irPR) and pre-treatment TLR4 using different cutoffs will be presented in 2x2 tables and the proportion of response will be compared between TLR4 high and TLR4 low patients using Barnard's unconditional exact test. Comparison of post treatment change in immunohistochemistry will be explored between G100 monotherapy 10  $\mu$ g and G100 monotherapy 20  $\mu$ g patients.

Association between clinical response and nanostring genes (NK, M1 Markers, M2 Markers, and other genes of interest) using PBMC and tumor samples will be explored using a logistic regression model that includes  $\log_2$  transformed nanostring data. Post/pre mean expression ratio (as antilogarithm of the means of ( $\log_2$  post –  $\log_2$  pre)) for responder and non-responder, odds ratio, and nominal and adjusted p-values will be presented. Adjusted p-value is adjusted using False Discovery Rate (FDR) method. Ten most upregulated and ten most downregulated immune-related genes will be presented, with post/pre mean expression ratio and p-value from signed-rank test. Further, ten most highly differentially induced immune-related genes in clinical responders versus non-responders will be explored.

T cell receptor (TCR) clones not detectable at baseline in tumor/PBMC but become detectable or increased post-treatment in tumor/PBMC will be explored.

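### Minor response stops below 50%, so if SAP 5.6.8 uses confirmed irPR, an unconfirmed 60% decrease fails the exploratory irPR+MR endpoint while a 30% decrease passes

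*SAP*

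**What the plan says.** SAP 5.6.2 sets the categories. An irPR is a decrease in tumor burden of at least 50% "relative to baseline, confirmed by a consecutive assessment at least 4 weeks from first documentation". An irSD is whatever is left: "not meeting criteria for irCR or irPR, in absence of irPD". Minor response is a band with a ceiling: "MR (minor response) is defined as more than 25% decrease in tumor burden but less than the 50% that would make it a PR". No confirmation rule is given for MR, and the text does not say whether it is judged on the best change or at any visit.

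The section also says "Both unconfirmed and confirmed response using irRC criteria will be reported", and for one of those two summaries it adds: "In confirmed ORR summary, patients with best response of unconfirmed irPR will be summarized as irSD".

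MR is then used in three places. It defines response subgroups in 5.6.2 and PFS subgroups in 5.6.4, in each case MR patients and MR patients with an abscopal decrease. In 5.6.8 it is pooled with irPR in a logistic regression: "Association between clinical endpoints (irPR, irPR+MR, irPR+MR+SD, abscopal best % change better than -25%) and cellular immunity by immunohistochemistry will be explored". Section 5.6.8 does not say whether its irPR is confirmed or unconfirmed.

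**The concern.** A pooled endpoint such as irPR+MR is meant to separate patients with more shrinkage from patients with less. That works only if the two categories adjoin. Here irPR has a confirmation condition and MR has a ceiling at 50%, so a best decrease of 50% or more that was never confirmed can fall between them. Such a patient would count as a failure although the tumor shrank more than that of an MR patient who counts as a success.

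At stake is the coding of the irPR+MR outcome in the immunohistochemistry regression, and the membership of the MR subgroups. There is also a reproducibility problem: two programmers working from the same SAP could build different irPR+MR variables.

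**Working it through.** The plan gives no sample size, power or expected rate for irPR+MR, so there is no figure to reproduce. The check applies the written definitions to example patients.

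**Inputs (SAP 5.6.2).** irPR: decrease of at least 50%, confirmed at least 4 weeks later. MR: decrease above 25% and below 50%. irPD: rise of at least 25% from nadir, confirmed at least 4 weeks later. irSD: none of irCR, irPR or irPD.

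**Step 1: coding of irPR+MR.** Entries are decreases from baseline on consecutive scans at least 4 weeks apart.

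| Patient | irPR confirmed, MR on best change | irPR confirmed, MR at any visit | irPR unconfirmed |
|---|---|---|---|
| 30% then 30% | pass (MR) | pass (MR) | pass (MR) |
| 60%, last scan | **fail** | **fail** | pass (irPR) |
| 60% then 40% | **fail** | pass (MR) | pass (irPR) |
| 60% then 10% | **fail** | **fail** | pass (irPR) |
| 60% then 60% | pass (irPR) | pass (irPR) | pass (irPR) |

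The inversion therefore depends on the reading. It occurs with confirmed irPR, is only partly relieved if MR may be met at any visit, and vanishes with unconfirmed irPR.

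**Step 2: which of these patients are really irSD?** Set baseline burden at 100. After a 60% decrease the nadir is 40, and the irPD threshold is 40 × 1.25 = 50. A scan that fails to confirm irPR has burden above 50, so after a decrease of 60% or more every non-confirming scan also reaches the irPD threshold. For 60% then 40% the rise is 60/40 - 1 = 50%; for 60% then 10% it is 90/40 - 1 = 125%. These two patients remain irSD only if the irPD is not confirmed.

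Two kinds of case are clean:
- a deep decrease on the last available scan, with nothing after it;
- a best decrease between 50% and 60% that slips back slightly. For 55% then 45%, burden goes from 45 to 55, a rise of 55/45 - 1 = 22.2%, which is below 25%. This patient is irSD, and is outside MR on best change.

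**Step 3: reach.** Take the patient at -60% on the last scan. The irPR endpoint does not use MR. In irPR+MR+SD the patient counts under every reading, as irPR or as irSD. The abscopal endpoint has a threshold of -25% and no ceiling. ORR does not use MR, and CBR includes stable disease. DOR includes unconfirmed responders: "DOR analysis will include only patients with confirmed/unconfirmed response of irCR/irPR using irRC".

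**The case against.** The strongest reply is that the SAP does not apply the confirmed classification everywhere. The sentence moving unconfirmed irPR to irSD is limited to the confirmed ORR summary, unconfirmed response is reported alongside it, and DOR counts both. The MR definition itself speaks of 50% as the level that makes a PR, which suggests adjoining categories. Since 5.6.8 is silent, its irPR may be the unconfirmed one.

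This stands to the extent that the inversion is conditional. It does not remove the gap. The only written irPR definition, in SAP 5.6.2 and in protocol Appendix B, includes confirmation. The residual irSD definition gives the same result without the reclassification sentence. Where the SAP wants unconfirmed responses, as in 5.6.3, it says so; 5.6.8 writes plain irPR.

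Other parts of the reply also stand. Coding a quickly reversed shrinkage as non-response is defensible, and Step 2 shows that many non-confirming patients would be at the progression threshold. The plots of percentage change in 5.6.1 show deep decreases whatever their confirmation status. The affected model is exploratory, with nominal p-values under SAP section 8.

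A reader might also infer that unconfirmed responses must be common, because scans are 8 weeks apart in the first year and the sponsor terminated the study. The documents do not support this. Confirmation needs a scan at least 4 weeks later, so the next routine scan serves. SAP section 9 gives termination as the reason for dropping the Lugano and independent-review analyses; it does not report missing confirmatory scans. Termination could leave some last-scan responses unconfirmed, but no count is given.

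**Conclusion.** The definitions in SAP 5.6.2 leave an unconfirmed decrease of 50% or more outside both irPR and MR. If 5.6.8 uses that irPR definition, such a patient is coded a failure for irPR+MR while a patient at -30% is coded a success. The same patient is absent from the MR subgroups in 5.6.2 and 5.6.4. The effect is confined to one exploratory endpoint and those subgroups.

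Two stronger conclusions do not follow. A reader might take the inversion as certain, but 5.6.8 does not say which irPR it uses. A reader might also conclude that every marker association is attenuated, but three of the four endpoints in that sentence are untouched by the gap.

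For irPR+MR itself the size is unknown. As a scenario only, assume 40 patients, 30% of them with decreases of 50% or more, 25% with MR, and a marker-shrinkage correlation of 0.45. If 10%, 20% or 30% of the deep decreases are unconfirmed, 40 × 0.30 × 0.10, 0.20 or 0.30 = 1.2, 2.4 or 3.6 patients are affected. Simulated power of the irPR+MR model (likelihood-ratio test at 5%, 2,000 trials per setting) then falls from about 66% to 57%, 48% or 41%. None of these inputs is in the documents. The simulation also assumes that, given shrinkage, confirmation is unrelated to the marker. If the marker tracks durable response, coding transient shrinkage as failure need not attenuate anything.

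**What to change.** In SAP 5.6.2, define MR as a best decrease in tumor burden of more than 25% in a patient who does not meet irPR or irCR under the classification in use. With confirmed response, an unconfirmed decrease of 50% or more then counts as MR; with unconfirmed response it is already irPR. Either way, the patient at -60% on the last scan and the patient at -30% both meet irPR+MR. In 5.6.8, state whether irPR is confirmed or unconfirmed.

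The cost is a sentence in each section and a change to the derived MR flag. There is a small downside: the flag now depends on the classification, so it must be derived for each one used, and some unconfirmed deep decreases, including some that reversed, will carry the label minor.
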